### 2.1.2 Data Collection

Data collection will occur at three time points: at baseline and again at 6 and 12 months of follow-up. During each assessment, participants will complete self-administered questionnaires on tablets or smartphones via the Qualtrics platform. For individuals assigned to the STOS group, HIV self-testing outcomes will be documented by a trained counselor and stored in an encrypted file with restricted access. Only the Principal Investigator (PI) and the Study Statistician will be authorized to view these data to maintain strict confidentiality.

All study data will be housed on secure institutional servers in encrypted, password-protected formats to ensure robust data security.

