## 2.5 Assessment and management of risk

This study will be conducted as a low-risk observational cohort study. However, certain items in the questionnaire, such as those related to sexual behavior or HIV status, may be considered sensitive. To minimize potential risks, several protective measures will be implemented. All data will be collected anonymously and stored securely using an encrypted system with restricted access, ensuring that no personally identifiable information is recorded.

Participants will be informed of their right to skip any question they find uncomfortable and their right to withdraw from the study at any time without any negative consequences. Additionally, counsellor will provide continuous support by explaining study procedures and addressing participants' questions throughout the study period. If necessary, participants will be referred to mental health or HIV-related services for appropriate care.

In cases where participants are found to be HIV positive, they will receive preliminary counseling and be referred to appropriate healthcare facilities for further testing and treatment in accordance with the Ministry of Public Health guidelines.

A Data and Safety Monitoring Board (DSMB) will also be established to oversee the project's risk management strategies, monitor participant safety and well-being, and ensure continuous ethical compliance. The DSMB will operate independently to review study procedures and provide recommendations to the research team regarding any necessary protocol adjustments to maintain ethical and safety standards throughout the study.

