#### 3.4 Secondary Outcomes

- **HIV incidence:**

Number of new HIV infections per 100 person-years, based on STOS testing results and self-reported data during follow-up.

- **Sexual risk behavior:**

Proportion of participants reporting condomless anal intercourse with male partners during the past 6 months, measured through self-reported survey data.

- **Health-related risk behaviors (mental health and substance use):**

Proportion of participants reporting mental health problems (e.g., depressive symptoms, suicidal risk) and frequency of substance use during the past 6 months, based on self-reported survey data.

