## 5.2 Data Cleaning and Preparation

After exporting the data from Qualtrics, the research team will conduct structured cleaning procedures using STATA command scripts to ensure accuracy and consistency. Key tasks will include identifying outliers, detecting logically inconsistent answers, checking the correctness of skip patterns, and verifying that numerical variables fall within acceptable ranges. Variables that depend on previous responses will also be reviewed to confirm internal coherence.

For the preparation of the analytic dataset, information from two sources will be combined: (1) the self-administered online questionnaires collected through Qualtrics, and (2) HIV self-testing outcomes obtained from participants in the STOS intervention group. These datasets will be harmonized before merging. To ensure accurate linkage across time points, participants will be asked to provide the same nickname or pseudonym during every round of data collection.

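### The SAP bases HIV incidence on unconfirmed self-test results and self-report, so a false-reactive test may be counted as a new infection, from study tests in the STOS arm only

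*Combined protocol and SAP*

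**What the plan says.** - **Endpoint.** SAP 3.4 gives HIV incidence as "Number of new HIV infections per 100 person-years, based on STOS testing results and self-reported data during follow-up". It has no case definition, no confirmation step and no rule for sources that disagree.
- **Test.** Protocol section 2 describes a rapid antibody/antigen self-test done with a counsellor on video. Its specificity is not given.
- **After a positive result.** Protocol 2.5 says of participants found positive that "they will receive preliminary counseling and be referred to appropriate healthcare facilities for further testing and treatment".
- **What is recorded.** Under Protocol 2.1.2, for the STOS arm, "HIV self-testing outcomes will be documented by a trained counselor". No facility result is mentioned.
- **What is merged.** In SAP 5.2, "information from two sources will be combined": "the self-administered online questionnaires collected through Qualtrics" and "HIV self-testing outcomes obtained from participants in the STOS intervention group".
- **Sensitivity analyses.** SAP 7 varies the model, the link function and the estimation approach. It does not vary the outcome definition.
- **Status.** SAP 3.4 lists incidence as secondary. Protocol 2.4.2 lists new infections among the primary outcomes.

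**The concern.** The protocol does not stop at the self-test: it sends a man with a positive result for more testing. The analysis plan has no named place for what that testing finds. An analyst following SAP 3.4 and 5.2 would hold the counsellor's record of the self-test and whatever the questionnaire happens to contain. For a man whose self-test was reactive and whose facility result was negative, nothing written says he is not a case.

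The error would not fall equally on the arms. Study self-test results exist only for STOS, and control cases rest on self-report. False-reactive study tests can therefore only raise the STOS rate, which pushes the rate ratio against the intervention. With only a handful of infections expected, one misclassified man changes the estimate visibly.

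**Working it through.** The documents give no event count, power figure or specificity for HIV incidence, so there is no stated figure to reproduce. The calculation below is an illustration.

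**Inputs from the documents**
- STOS arm of 50 men followed for 12 months (SAP 2): 50 × 1 = 50 person-years with no loss.
- Retention expected above 80% (Protocol 2.1.3): 50 × 0.8 = 40 person-years as a rough lower case.
- Target of a test at least every six months (SAP 1.2): about 2 tests per man, or 100 tests. The number of STOS sessions is not stated.
- Incidence of 5.8% among young MSM in Hanoi (Protocol 1.1). The unit is not given; it is read here as per year.

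**Assumption**
- Specificity of 99.0% to 99.9%.

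**Step 1: weight of one case.** 1/50 = 2.0 per 100 person-years; 1/40 = 2.5 per 100 person-years.

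**Step 2: expected true infections.** 50 × 0.058 = 2.9.

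**Step 3: false-reactives.** Expected number = tests × (1 − specificity). Chance of at least one = 1 − specificity^tests. Rate if all are counted = (2.9 + false-reactives)/50. For 100 tests:

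| Specificity | Expected false-reactives | Chance of at least one | STOS rate per 100 person-years | Inflation |
|---|---|---|---|---|
| 99.9% | 0.1 | 9.5% | 6.0 | 1.03 |
| 99.8% | 0.2 | 18% | 6.2 | 1.07 |
| 99.5% | 0.5 | 39% | 6.8 | 1.17 |
| 99.0% | 1.0 | 63% | 7.8 | 1.34 |

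**Step 4: how far the assumptions move this.**
- At 80% retention (80 tests): 0.08 to 0.8 expected, with a chance of at least one of 7.7% to 55%.
- At one test per man and 80% retention (40 tests): 0.04 to 0.4 expected.
- At three tests per man with no loss (150 tests): 0.15 to 1.5 expected, with a chance of at least one of 14% to 78%. The extreme corner gives 1.5/(1.5 + 2.9) = 34% of counted cases.
- If true incidence were 2 per 100 person-years (assumed), 1.0 true infection is expected. At 100 tests the inflation is then (1.0 + 0.1)/1.0 = 1.10 to (1.0 + 1.0)/1.0 = 2.0.

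**Step 5: effect of confirmation.** If only confirmed infections count, the false-reactive term falls to about zero and the expected STOS rate returns to 2.9/50 = 5.8 per 100 person-years.

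**The case against.** A reader might infer four stronger things that the documents do not support.

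- *That the SAP counts every reactive self-test as an infection.* SAP 3.4 says what the endpoint is based on and gives no counting rule. Counting on the self-test alone is a natural reading but remains an inference.
- *That the facility result can never reach the dataset.* Self-report is a named source, and the questionnaire is repeated at 6 and 12 months, so a man could report his later result there. The items are not in the documents and cannot be assumed absent. SAP 5.2 also plans to check for inconsistent answers and to harmonise the two sources.
- *That Protocol 2.5 calls the self-test result preliminary.* That word describes the counselling. The further testing may well be confirmatory, but the text does not say so.
- *That a third of counted cases would be false.* The 34% and 78% figures need 99.0% specificity, three tests per man and no loss to follow-up.

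The consequence is also limited. In a pilot of this size the comparison is imprecise anyway: three events in 50 person-years have an exact 95% interval of about 0.62/50 to 8.77/50, or 1.2 to 17.5 per 100 person-years. The bias runs against STOS, so it cannot produce a false benefit.

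Confirmation alone would not make a case new. No baseline HIV test is described; Protocol 2.1.1 only says that men found positive after the survey are not invited. At the 17% prevalence that Protocol 1.1 gives for Ho Chi Minh City, up to 50 × 0.17 = 8.5 STOS men could already be infected. This is an upper bound that ignores the exclusion.

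All of this narrows the point, but the gap remains. No text plans to collect the facility result, and none says which source prevails when a recorded reactive test and a later report disagree.

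**Conclusion.** The concern holds in a limited form. The incidence endpoint requires no confirmation, the result needed to classify a case is not a named data source, and no rule reconciles the self-test, the facility result and self-report. A false-reactive study test may therefore be counted as an infection, and only in STOS. At two tests per man the expected number is small, 0.1 to 1.0, but a single case adds 2.0 per 100 person-years, about a third of the 5.8 background figure (2.0/5.8 = 34%).

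These sizes rest on an assumed specificity, an assumed number of tests, no loss to follow-up and a Hanoi figure read as an annual rate. The structural gap depends on none of them. It should be corrected because it is cheap to do so, and because the protocol gives this outcome primary standing.

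**What to change.** - **Case definition (SAP 3.4).** An incident case is a reactive self-test or a self-reported positive that is confirmed at the referral facility, in a man with a negative result at or before the start of follow-up. Positives at a first test with no earlier negative are shown separately as possibly prevalent.
- **Data capture.** Record the facility result (positive, negative or not obtained) in the STOS file, and ask the same item in the follow-up survey of both arms.
- **Merge and precedence (SAP 5.2).** Add this result to the merge and state that it prevails over the self-test. A man whose facility result is negative stays uninfected and keeps contributing person-time.
- **Reporting.** Give the rate with and without unconfirmed cases.
- **If data collection is already complete.** Some text in Protocol 2.3.2 and section 4 is in the past tense, which suggests it may be. The definition and the two-way reporting can still be added, and the facility result sought for the few positive participants.

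The cost is one added field and one survey item. The referral is already planned, so only outcome classification and data capture change. Some cases will remain unconfirmed, and earlier negatives in the control arm may rest on self-report.

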## 1. Introduction

### 1.1 Overview of the Problem

HIV infection among men who have sex with men (MSM) in Vietnam continues to rise, with prevalence in Ho Chi Minh City (HCMC) estimated at 17% and incidence among young MSM (YMSM) in Hanoi at 5.8%. Behavioral risks such as unprotected sex, multiple partners, and untreated STIs sustain high levels of circulating virus within MSM networks. Low HIV testing rates and poor engagement in care further exacerbate transmission. Meanwhile, widespread smartphone and internet use among Vietnamese MSM offers an opportunity for online testing innovations.

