### 1.2 Supporting Evidence

National surveillance shows that HIV prevalence among MSM increased from 6.2% in 2006 to 14% in 2009 in HCMC, reaching 19% nationwide by 2011. Epidemiological studies identify consistent risk factors including low HIV knowledge, sexual risk and STIs, identity- and stigma-related challenges, and limited access to appropriate health services. A Vietnam-based survey found that 76.5% of MSM had never been voluntarily tested for HIV. Evidence from Thailand demonstrates that an online HIV testing (OHT) model achieved 90% retention and 100% linkage to care. Additionally, 97% of Vietnamese MSM report HIV self-testing as acceptable.

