## 2. Study design and methods of data collection

This study aims to evaluate the effectiveness of the HIV self-testing with online supervision (STOS) intervention, which includes the introduction of a HIV rapid diagnostic antibody/antigen-based self-testing conducted with the support of a trained counsellor via video conferencing, among young men who have sex with men (YMSM) aged 16–29 years.

The study employs a pilot randomized controlled trial (RCT) design with two groups: an intervention group (STOS) and a control group. The total sample size is 100 participants (50 per group). The follow-up period spans 12 months, with data collected at three time points: baseline, 6 months, and 12 months.

Data collection includes self-administered online questionnaires completed through the Qualtrics platform. For participants in the intervention group, the study involves the implementation of real-time online supervised HIV self-testing conducted by a trained counsellor through video conferencing.

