### 2.1.3 Retention and Engagement Strategies

To ensure sustained participation throughout the follow-up period, the research team will implement continuous engagement measures using multiple digital communication channels, including the Zalo application, SMS, telephone calls, and support from community peer leaders. Participants will be contacted regularly to receive project updates, appointment reminders, and encouragement to take part in each data-collection round. Ongoing assistance will also be provided to help maintain participants' motivation and consistency in completing questionnaires. For the STOS group, follow-up communication will additionally ensure that participants receive their self-testing kits. These combined strategies are expected to achieve follow-up retention rates exceeding 80% at each assessment point.

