## 2. Study Design Overview

This study is a pilot randomized controlled trial (pilot RCT) using a longitudinal cohort design among young men who have sex with men (YMSM) aged 15–29 years, with a total of 100 participants equally allocated into two groups:

- STOS intervention group (n = 50)
- Control group (n = 50)

Participants will be followed for a period of 12 months, with data collection conducted at three times: baseline, 6 months, and 12 months of follow-up.

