## 6.2 Primary and Secondary Outcome Analyses

Generalized Estimating Equations (GEE) with appropriate link functions (e.g., logit for binary outcomes, identity for continuous variables) will be applied to assess intervention effects

over time. Each model will include study arm, follow-up time, and an interaction term to estimate differential changes between groups. Robust standard errors will be used to account for correlations within individuals. Person-time will also be calculated, and rate ratios with 95% confidence intervals will be reported.

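### HIV incidence is reported per 100 person-years, but person-time is not defined or tied to HIV testing, so the rates and the rate ratio depend on how much each arm tests

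*Combined protocol and SAP*

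**What the plan says.** SAP 3.4 lists HIV incidence as a secondary outcome: "Number of new HIV infections per 100 person-years, based on STOS testing results and self-reported data during follow-up". Protocol 2.4.2 calls the rate of new infections a primary outcome. The only sentence on the denominator is in SAP 6.2: "Person-time will also be calculated, and rate ratios with 95% confidence intervals will be reported". No start, stop or censoring rule is given.

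The only follow-up described is the survey schedule. SAP 2 says: "Participants will be followed for a period of 12 months, with data collection conducted at three times: baseline, 6 months, and 12 months of follow-up". SAP 4.1 keeps every allocated man with a baseline assessment, whatever his later engagement.

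On how infections come to light:

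- SAP 5.2 names study-recorded test outcomes for the STOS arm only.
- Controls receive a venue-testing voucher (protocol 2.1.1) or information about free testing (protocol 2.3.1). Protocol 2.4.2 describes them as completing questionnaires only.
- Protocol 2.1.1 does not invite men found to be HIV-positive after the survey, but no baseline HIV test is described for either arm.

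**The concern.** A new infection enters the numerator only through a test: a STOS session, or an outside test that the man reports. A questionnaire answered without a test says nothing about infection. If person-time runs to month 12 for everyone, a man who never tests adds a full event-free year, and a man last tested at month 6 adds half a year in which no infection could be seen. Both are scored as confirmed negative for that time.

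The start of person-time is also open. Without a documented negative test, an infection already present at entry and found at the first test can be counted as new.

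The two errors pull in opposite directions, and both scale with testing. Testing uptake is the SAP's primary outcome and the behaviour STOS is meant to change, so the errors will not be equal in the two arms. A difference in incidence could then reflect testing alone.

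**Working it through.** The documents give no expected number of infections and no incidence calculation, so there is no planned figure to reproduce. The checks below ask what the incidence formula returns when the true rate is known and equal in both arms.

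**Inputs from the documents.** 50 men per arm and 12 months (protocol 2); incidence of 5.8% in young MSM in Hanoi (protocol 1.1), read here as 5.8 per 100 person-years, which is an assumption about the unit. **Other assumptions:** no dropout, and the testing patterns stated below.

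**Check 1: closed form.** Infection times are exponential with λ = 0.058 per year. Probability of infection by 12 months: 1 − e^(−0.058) = 0.05635; by 6 months: 1 − e^(−0.029) = 0.02858. Mean infection-free years: 0.05635/0.058 = 0.9716 over 12 months and 0.02858/0.058 = 0.4928 over 6 months. Full testing would give 50 × 0.05635 = 2.8 infections per arm.

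Split each arm by last test (12 months / 6 months / none), with nobody infected at entry. A man last tested negative at 6 months still adds the other half-year under a follow-up denominator, so his group averages 0.4928 + 0.9714 × 0.5 = 0.9785 years.

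- 90/5/5%: infections seen = 50 × (0.9 × 0.05635 + 0.05 × 0.02858) = 2.61. Follow-up years = 50 × (0.9 × 0.9716 + 0.05 × 0.9785 + 0.05) = 48.67. Rate = 2.61/48.67 = 5.36 per 100. Years up to the last test = 44.95; rate = 5.80.
- 40/20/40%: infections seen = 50 × (0.4 × 0.05635 + 0.2 × 0.02858) = 1.41. Follow-up years = 49.22. Rate = 2.87. Years up to the last test = 24.36; rate = 5.80.

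If STOS follows the first pattern and controls the second, the rate ratio is 5.36/2.87 = 1.87 with no true effect. With time ended at the last test it is 1.00.

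Now let 5% carry an undiagnosed infection at entry that is counted as new when first tested, with denominators unchanged:

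- 90/5/5%: (2.61 × 0.95 + 50 × 0.95 × 0.05)/48.67 = 9.97.
- 40/20/40%: (1.41 × 0.95 + 50 × 0.60 × 0.05)/49.22 = 5.77.

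Undiagnosed infection of about 0.5% in the first pattern, or 5.0% in the second, cancels the understatement exactly. The sign is therefore not known in advance.

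**Check 2: simulation of dated tests** (2,000,000 men per scenario). STOS tests fall near 0, 6 and 12 months, each attended with the stated probability. Control tests fall at a uniform time in each six-month window with the stated probability. Follow-up rate = positives divided by time to detection or 12 months. Tested-interval rate = new infections after a first negative test, divided by time from that test to the last test (midpoint between last negative and first positive for an infection).

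| Pattern | Follow-up rate, none infected at entry | Follow-up rate, 5% infected at entry | Tested-interval rate |
|---|---|---|---|
| STOS, 80% attendance | 5.0 | 10.2 | 5.8 |
| STOS, 100% attendance | 5.7 | 11.1 | 5.8 |
| Controls, 50% per window | 2.5 | 6.3 | 5.8 |
| Controls, 80% per window | 3.7 | 8.6 | 5.7–5.9 |

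Hand check for controls at 50%: mean time of last test = 0.5 × 0.75 + 0.5 × 0.5 × 0.25 = 0.44 years, and 0.44 × 5.8 = 2.5.

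With no true effect, the STOS-to-control ratio runs from 5.0/3.7 = 1.4 to 5.7/2.5 = 2.3 with nobody infected at entry, and from 10.2/8.6 = 1.2 to 11.1/6.3 = 1.8 with 5% infected.

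**Check 3: does the tested interval need an assumption?** Yes. With control testing at 50% per window, if infected men test at 75% the tested-interval rate is 8.7; if they test at 25% it is 2.9. It returns 5.8 only when testing is unrelated to infection.

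**The case against.** The strongest reply is that the SAP does not state a wrong denominator; it states none. In SAP 3.4 the words about follow-up describe where the data come from, and an analyst could end person-time at the last test without departing from the plan. That is correct, so the defect is a missing definition. It still matters, because survey follow-up is the only follow-up described and SAP 4.1 keeps untested men in.

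A reader might infer three stronger claims that the documents do not support:

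- *Each arm's incidence is understated.* This holds only if nobody is infected at entry, and no baseline test secures that.
- *The STOS rate would be cut by half or more.* A rate of 2.3 to 2.9 arises only if there is no month-12 session. Protocol 2.3.1 speaks of STOS sessions at follow-up rounds. With a month-12 session and nobody infected at entry, the shortfall is about 1 to 13%.
- *Controls would read about 1.3.* That needs 23.5% testing per six-month window, taken from the cited finding that "76.5% of MSM had never been voluntarily tested for HIV". A lifetime figure gives no six-month probability, and controls are offered a voucher.

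Precision is also a fair point. Three infections in 50 person-years have an exact 95% interval of about 1.2 to 17.5 per 100, far wider than the STOS shortfall just given. It does not excuse an error that differs by arm and would be read as an intervention effect.

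Finally, the tested interval conditions on the behaviour that STOS changes and departs from the full ITT set. That stands as a limitation to report.

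**Conclusion.** The concern holds as a missing definition with consequences. SAP 3.4 and 6.2 do not say what person-time is, and the natural reading yields rates that mix infection with testing. Under the assumed patterns and a true rate of 5.8 in both arms, the plan could report anything from 2.5 to about 11 per 100 person-years, and a rate ratio of about 1.2 to 2.3 against STOS where the truth is 1. The direction of error within one arm cannot be stated without knowing undiagnosed infection at entry. The sizes rest on the assumed testing patterns, the reading of 5.8% as a yearly rate, no dropout, and 0 to 5% undiagnosed infection at entry. With about three infections expected per arm, the comparison is descriptive under any denominator. The change is worth making because reducing incidence is a stated objective in SAP 3.2 and a primary outcome in protocol 2.4.2.

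**What to change.** In SAP 3.4 and 6.2:

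- Start a man's person-time at his first negative HIV test in the study. End it at his last test or, for a new infection, at the midpoint between the last negative and first positive test.
- Report positives at a first test separately, and not as incident.
- Report by arm the men and person-years contributing, and the number not tested.
- Take dates from STOS session records. At the 6- and 12-month questionnaires, ask all men the month and result of each HIV test since the last round.
- Call the incidence comparison descriptive, and state with the result that it is biased if testing is related to infection risk.

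The cost is a few SAP sentences and one or two questionnaire items, with no added tests or participants. The price is information. A control needs two tests, on average half a year apart, so 50 controls give roughly 50 × 0.235² × 0.5 = 1.4, 50 × 0.5² × 0.5 = 6 or 50 × 0.8² × 0.5 = 16 person-years at 23.5, 50 or 80% testing per window. Fifty STOS men with a month-12 session give about 37 to 48. Intervals will be wider, the control rate may be unusable, and this outcome will no longer use the full ITT set.

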#### 2.4.2 Primary and Secondary Outcome Analyses

To evaluate the effects of the STOS intervention, two groups will be compared: the STOS group, who receive an HIV self-testing kit and complete the online questionnaires, and the control group, who complete the questionnaires only. The primary outcomes are the rate of HIV testing uptake and the rate of new HIV infections during the study period. The secondary outcomes include changes in sexual behaviors, mental health, and other psychosocial indicators over time. To assess the effects of the intervention across time points, Generalized Estimating Equations (GEE) models will be applied, using a log link function for rate outcomes and an identity link function for continuous outcomes. The models will include variables for study arm (STOS vs. control), time (follow-up round), and their interaction term (arm  $\times$  time) to estimate longitudinal intervention effects. Robust standard errors will be used to account for within-subject correlation due to repeated measures. The results will be presented as Rate Ratios (RRs or Incidence Rate Ratios, IRRs) with 95% confidence intervals (CIs) and p-values to indicate the magnitude and statistical significance of the observed effects.

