## 5.3 Variable Coding and Labeling

All variables will be coded and labeled according to a standardized data dictionary to ensure consistency across all study rounds. Dichotomous variables will use fixed coding (e.g., 1 = Yes, 0 = No), and Likert-scale items will follow predefined response categories. Maintaining uniform coding conventions will facilitate accurate interpretation, allow meaningful comparisons over time, and improve the reproducibility of the analyses.

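### Depressive symptoms are analysed only as the proportion with an undefined problem; if a graded score is collected, analysing that score with the identity-link GEE already planned would use more of the data

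*Combined protocol and SAP*

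**What the plan says.** SAP 3.4 gives the mental-health outcome as "Proportion of participants reporting mental health problems (e.g., depressive symptoms, suicidal risk"), self-reported over the past six months. It names no questionnaire and no scoring rule, and does not say what counts as a problem. The matching objective in SAP 3.2 is to reduce mental health problems, with depression and suicidal risk given as the content.

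Protocol 2.4.2 describes the same domain more openly: "The secondary outcomes include changes in sexual behaviors, mental health, and other psychosocial indicators over time". It then assigns "an identity link function for continuous outcomes" within the GEE framework, without saying which outcomes are continuous. SAP 6.2 carries the same provision, "identity for continuous variables", alongside a logit link for binary outcomes, and fits arm, time and their interaction with robust standard errors. SAP 5.3 sets general coding rules for dichotomous variables and adds that "Likert-scale items will follow predefined response categories"; it does not link either type to mental health.

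On size and timing, protocol section 2 states "The total sample size is 100 participants (50 per group") and "data collected at three time points: baseline, 6 months, and 12 months". Protocol 2.1.3 says the engagement measures are "expected to achieve follow-up retention rates exceeding 80% at each assessment point".

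**The concern.** Depressive symptoms are often measured on a graded scale. If that is so here, a yes/no outcome treats a man whose symptoms improve greatly without crossing the cut as unchanged, and a man who moves one point across it as fully changed. The between-arm comparison becomes less precise, and this trial has little information to spare.

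The wording also leaves the cut open. With no threshold stated, the outcome cannot be programmed from SAP 3.4, and the threshold could be chosen after the data are seen. The model that would suit a score is already in both documents, but no mental-health outcome in SAP 3.4 is defined so as to use it.

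**Working it through.** **Figure in the plan.** There is no power figure to reproduce. The total of 100 is given without alpha, power, effect size or standard deviation.

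**Inputs from the documents.** 50 per arm (protocol section 2). Retention above 80% (protocol 2.1.3), so at least 0.80 × 50 = 40 per arm, and a working range of 40 to 50.

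**Inputs assumed, because the documents give none.** A graded depression score exists; it is normal with SD 1; standardised difference d = 0.2 to 0.6; 20 to 50% of controls lie above the cut; two-sided 5% (suggested by the planned 95% CIs); one follow-up visit; no multiplicity adjustment.

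**Formulas.**
- Full scale: two-sample t test, df = 2n − 2, noncentrality d·√(n/2).
- Dichotomised: with control proportion p1 above the cut, the same shift gives p2 = 1 − Φ(z₁₋ₚ₁ + d). Power = Φ[(p1 − p2 − 1.96·SE₀)/SE₁], where SE₀ is the pooled and SE₁ the unpooled standard error.

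**One cell in full (n = 40, d = 0.5, p1 = 0.30).**
- Full scale: noncentrality 0.5 × √20 = 2.24, df = 78, power 59.8%.
- Dichotomised: p2 = 1 − Φ(0.524 + 0.5) = 0.153 and p1 − p2 = 0.147. SE₀ = √(2 × 0.2264 × 0.7736/40) = 0.0936. SE₁ = √[(0.30 × 0.70 + 0.153 × 0.847)/40] = 0.0921. Power = Φ(−0.39) = 34.7%.
- Loss: 59.8 − 34.7 = 25.1 points.

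**Grid at 40 per arm** (losses from unrounded powers).

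| d | Full scale | Dichotomised, p1 from 20% to 50% | Loss in points |
|---|---|---|---|
| 0.2 | 14.3% | 8.7–10.5% | 3.8–5.6 |
| 0.3 | 26.3% | 14.0–18.3% | 8.0–12.3 |
| 0.4 | 42.4% | 20.7–28.8% | 13.6–21.6 |
| 0.5 | 59.8% | 28.5–41.3% | 18.5–31.3 |
| 0.6 | 75.5% | 36.8–54.6% | 20.9–38.7 |

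At 50 per arm, d = 0.3 to 0.6 gives losses of about 10 to 40 points.

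**Sensitivity to the assumptions.**
- Skewed scores: negative-binomial scores capped at 27 and cut at 10, dispersion 1 to 3, control means 7–8 against 4–5, 40 per arm, 20,000 simulated trials. The loss is about 6 to 20 points; for example, dispersion 2 and means 7 against 5 give 43% against 30%.
- Wider normal grid (d = 0.2 to 0.8, 10 to 50% of controls above the cut, z approximation for the full scale): about 4 to 61 points.
- Both versions adjusted for baseline (correlation 0.5 to 0.7, d = 0.3 to 0.5, 20 to 50% above the cut, simulated): about 13 to 53 points.

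**How much the full scale can do.** For 80% power, d ≈ 2.80 × √(2/n), which is 0.56 at 50 per arm and 0.63 at 40 per arm. Smaller effects would usually be missed on either scale.

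**The case against.** The strongest objection is that the documents never say a depression score is collected. SAP 3.4 speaks of reporting problems, which fits yes/no items as well as a scale, and SAP 5.3 is a generic coding rule. If the items are yes/no, nothing is being dichotomised, the power loss disappears and the main remedy cannot be applied. This stands, and it makes the recommendation conditional.

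A reader might infer that the SAP contradicts a continuous outcome defined in the protocol. The text does not support that. Protocol 2.4.2 never calls mental health continuous, and a binary outcome can also change over time; SAP 6.2 keeps change through the arm-by-time term. The same protocol sentence covers sexual behaviour, which the SAP also makes a proportion. Nor is the identity link necessarily without use, since the substance-use frequency in SAP 3.4 could take it.

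It can also be said that a proportion answers SAP 3.2 directly, that nothing in the documents supports any particular effect of supervised self-testing on depression, and that this is a secondary outcome in a pilot with no power target. All of that is fair, and it limits the weight of the point. It does not explain why a graded score, if held, should be cut at an unstated threshold when the model for analysing it whole is already planned.

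**Conclusion.** The point holds as a conditional improvement. SAP 3.4 offers only a proportion with no instrument or cut-off. If depressive symptoms are recorded on a graded scale, analysing the score is the better use of the same answers.

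Dichotomising lowered power in every scenario examined. The size is illustrative: roughly 8 to 40 points for d = 0.3 to 0.6 with normal scores, 20 to 50% of controls above the cut and 40 to 50 per arm; about 4 to 6 points at d = 0.2 with 40 per arm; about 6 to 20 points under the skewed scores tried. Only the sample size and the retention expectation come from the documents, and the figures model a single visit, not the planned repeated-measures GEE.

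A reader might go further and conclude that a null result would be largely an artefact of the binary scale. The figures do not support that: at 40 per arm even the full scale has 26%, 42% and 60% power for d = 0.3, 0.4 and 0.5, so null results would be common either way, mainly because the trial is small.

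**What to change.** In SAP 3.4, name the instrument for depressive symptoms and how it is scored. Then, before outcome data are examined by arm:

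- **If a multi-item or graded score is collected:** make the total score at 6 and 12 months the analysed outcome, using the identity-link GEE with robust standard errors already in SAP 6.2 and protocol 2.4.2. Report the between-arm mean difference with its 95% CI. Keep the proportion above the instrument's published cut-off, stated in advance, as a descriptive supplement.
- **If it is a single ordered item:** use ordinal (proportional-odds) regression, and report the odds ratio with its 95% CI in place of a mean difference.
- **If only yes/no items exist:** keep the proportion and state which answers count as a problem.
- **Suicidal risk:** leave it binary if it is collected as yes/no.

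Align protocol 2.4.2 with SAP 3.4 and 6.2 so that all three describe the same outcome and model.

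The cost is wording. Where a score is already collected, no participants, visits or questionnaire items are added. The small downside is that a mean difference speaks less directly to policy readers than a percentage, which the supplementary proportion covers.
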